2.3.2 Exclusion Criteria

1. Patients receiving ATG, Campath or other immunosuppressive T cell monoclonal antibodies within 28 days of screening for enrollment.
2. Patients with other uncontrolled infections. For bacterial infections, patients must be receiving definitive therapy and have no signs of progressing infection for 72 hours prior to enrollment. For fungal infections patients must be receiving definitive systemic anti-fungal therapy and have no signs of progressing infection for 1 week prior to enrollment.

Progressing infection is defined as hemodynamic instability attributable to sepsis or new symptoms, worsening physical signs or radiographic findings attributable to infection. Persisting fever without other signs or symptoms will not be interpreted as progressing infection.

3. Patients who are less than 28 days removed from their allogeneic hematopoietic stem cell transplant or who have received donor lymphocyte infusions (DLI) within 28 days..
4. Patients with active acute GVHD grades II-IV.
5. Active and uncontrolled relapse of malignancy

2.3.3 Informed Consent

The informed consent process will begin at recognition of subject eligibility and consent will be obtained per institutional practices before study therapy is initiated. Consent process will consists of two parts: a) screening consent and b) treatment consent

1. Screening consent: The screening portion consists of registering demographic data and patient eligibility data. The search for a suitable matched VST line is initiated if the patient is eligible. If a VST line is not available, the following data will be collected: demographic data, HLA type, infection type and outcome data.
2. Treatment Consent: If a suitable matched VST line is available, the principal investigator or designee discusses the available line with the treating physician. After enrollment in the treatment portion of the protocol the patient can then receive the identified VST line if eligibility criteria are still met.

2.3.4 Donor Eligibility

2.3.4.1 The VST lines that will be used in this third party study derive from two sources

CHARMS Protocol v1.0 (10.30.13)	Version 5.0 (10.6.15)
Version 2.0 (12.09.13)	Version 6.0 (08.29.16)
Version 2.1 (03.07.14)	Version 7.0 (04.26.17)
Version 3.0 (06.17.14)	Version 8.0 (05.24.17)
Version 4.0 (11.06.14)	Version 9.0 (08.10.17)

A) Lines that were previously manufactured for our IRB approved protocol H29966. These donors were initially chosen as transplant donors because they were the best match with the original transplant recipient and they met eligibility criteria. There are either additional vials available after the product was used in the donor-specific setting, or was not infused either because the original recipient did not need the VSTs or the original recipient was ineligible. These donors gave consent for lines not used for the original recipient to be used in the third party setting.

B. Additional lines manufactured for third party use from individuals with common HLA types on an IRB approved protocol. Some of these individuals will be subjects who have previously enrolled on our IRB approved research study (H7634) to manufacture CTL lines from normal donors for preclinical studies so that we know that their lines have broad antiviral reactivity. We will approach these donors previously enrolled on this study to ascertain if they are willing to enroll and donate blood for the current study. We may also collaborate with the National Marrow Donor Program, which is a registry of HLA-typed donors who have volunteered for transplant donation to obtain additional donors. Those donors will be procured on a separate procurement protocol.

For all third party lines, donors have been evaluated by the director of the donor center at BCM or an NMDP donor physician for NMDP donors. Donors must meet standard eligibility criteria for donation of blood or marrow. They have been screened with the standard blood bank donor questionnaire, medical history and testing for infectious disease markers by a physician who is experienced in screening transplant donors. Only donors who have cleared this process and were deemed to be eligible provided blood for VST generation. For lines that were previously manufactured for H29966, only those where the donor is eligible may be included in the third party bank.

The results of the physician assessment and ID testing were reviewed by a CAGT laboratory director who gave the final eligibility determination according to the SOP for Donor Evaluation.

The processes discussed in the protocol and related manufacturing SOPs are in compliance with 21CFR1271.

2.4 Treatment Plan

2.4.1 VST Line selection and availability

2.4.1.1 VST Lines selection

We will use multivirus-specific VSTs, generated initially for use on our donor-specific study. The lines were generated using a rapid protocol whereby clinical grade pepmixes spanning immunogenic antigens from each of our target viruses are used to directly stimulate PBMCs, followed by expansion in the presence of growth promoting cytokines and the G-Rex culture device optimized for T cell expansion. Donor-specific VST lines generated according to this protocol were previously found to be safe and effective in a Phase I clinical trial as discussed.

To initiate the multivirus-specific VSTs 15×10^6 PBMCs were pulsed with a master mix of pepmixes spanning Adv (Hexon and Penton), CMV (IE1 and pp65), EBV (LMP2, EBNA1, BZLF1), BK virus

CHARMS Protocol v1.0 (10.30.13)	Version 5.0 (10.6.15)
Version 2.0 (12.09.13)	Version 6.0 (08.29.16)
Version 2.1 (03.07.14)	Version 7.0 (04.26.17)
Version 3.0 (06.17.14)	Version 8.0 (05.24.17)
Version 4.0 (11.06.14)	Version 9.0 (08.10.17)

(VP1 and large T) and HHV6 (U90, U11 and U14). After 30mins the cells/pepmix combination was transferred directly to the G-Rex culture device. The VST media was supplemented with the cytokines IL7 and IL4 (10ng/ml and 400U/ml, respectively) in order to inhibit apoptosis and promote expansion of multivirus-specific T cells.

The VST lines were checked for identity, phenotype and sterility, and cryopreserved prior to administration according to our SOP. To test the functional antigen specificity of the VST we will use individual pepmixes spanning each of the viral antigens used in the initial stimulation as a stimulus in IFN γ ELIspot. Epitope mapping will be performed using known HLA epitope peptides or peptide mini-pools to identify novel immunogenic epitope peptides within our target antigens.

Products that meet study specific release criteria, as detailed on the CofA, will be infused as per Section 2.4.2.

If a positive sterility testing result is reported after the product is infused, the FDA and other relevant parties will be notified as per our manufacturing SOP B01.03.XX (Product Quality Assurance Program and Release and Return of Clinical GMP/GTP Products) and clinical research SOP J02.06.XX (Serious Adverse Experience and Unanticipated Problem Reporting). Management of such a situation is further described in our SOP F05.09.XX (Management of Culture Positive Cell Therapy Products).

2.4.1.2 No Matched VST Line Available

If no matched line is available the patient will be registered so that the feasibility of the approach can be assessed.

2.4.1.3 VST Line Available but Patient Status Changes

Patients with a clinical course that changes between screening and infusion and renders patient ineligible at time of infusion will not be given the VST.

2.4.1.4 Criteria for Selection of VST Line

In general preference will be assigned to the infusion of a line with confirmed virus-specific activity against the infecting virus through a shared HLA allele rather than the overall level of HLA match. For example for a patient with an adenovirus infection a line that matches at 2 loci but that has recognition of adenovirus mediated through those antigens would be preferable to a line matched at 3 loci but with no demonstrated activity against adenovirus. Patients with a partial response are eligible to receive up to 4 additional doses.

2.4.2 Administration and Monitoring

2.4.2.1 Partially HLA-matched VSTs will be thawed and given by intravenous injection. Patients will receive 2×10^7 partially HLA-matched VSTs/m² as a single infusion. In the rare case where insufficient banked cell product is available, a lower number of cells may be infused after discussion with the principal investigator, patient and/or guardian and the treatment team.

2.4.2.2 Premedications: Patients without prior history of reaction to blood products generally do not require premedication. If patients receive premedication, Benadryl 0.25-0.5mg/kg (max 25 mg) IV/po and/or Tylenol 5-10 mg/kg (max 650 mg) po/iv may be given.

CHARMS Protocol v1.0 (10.30.13)	Version 5.0 (10.6.15)
Version 2.0 (12.09.13)	Version 6.0 (08.29.16)
Version 2.1 (03.07.14)	Version 7.0 (04.26.17)
Version 3.0 (06.17.14)	Version 8.0 (05.24.17)
Version 4.0 (11.06.14)	Version 9.0 (08.10.17)

2.4.2.3 Patients will be monitored according to institutional standards for administration of blood products and at a minimum will be monitored according to below:

- Patients should remain in the clinic for at least one hour
- Patients should remain on continuous pulse oximetry for at least 30 minutes
- Vital signs should be monitored at the end of infusion then at 30 and 60 minutes

2.4.2.4. Supportive Care: Patients will receive supportive care for acute or chronic toxicity, including blood components or antibiotics, and other intervention as appropriate.

2.4.2.5 If a patient 1) receives medication (such as steroids), which may affect the persistence or function of the infused VST, or 2) does not have a complete response to their initial infusion, did not experience a significant toxicity to their initial infusion, and if alternative treatment options are not available or associated with unacceptably high risk of side effects (e.g. count suppression or renal disease), they are eligible to receive up to 4 additional doses at the same initial dose at day 28 post-infusion and at a minimum 2 week interval thereafter. If the additional doses are post steroid administration, the steroid dose must be decreased to a dose of 0.5 mg/kg/day of Prednisone (or equivalent) or lower before the patient may receive additional doses.

Additional doses may be from the same donor or a different donor based on available cell lines and patient/disease factors. Decision to switch to a different donor can be made by the principal investigator based on factors that include sequential treatment of different viral infections, concerns for immune escape of the targeted virus and/or availability of a better matched or otherwise superior VST line. Additional treatments will only be given following the agreement of the patient, treating physician, and investigator. This process can be repeated as needed.

CHARMS Protocol v1.0 (10.30.13)
 Version 2.0 (12.09.13)
 Version 2.1 (03.07.14)
 Version 3.0 (06.17.14)
 Version 4.0 (11.06.14)

Version 5.0 (10.6.15)
 Version 6.0 (08.29.16)
 Version 7.0 (04.26.17)
 Version 8.0 (05.24.17)
 Version 9.0 (08.10.17)

2.5 Risks and Toxicities

2.5.1 Graft Versus Host Disease (GVHD)

The risk that adoptively transferred partially HLA-matched VSTs will cause Grade II or higher GVHD is low according to data from previous studies with 3rd party VSTs specific for adenovirus, EBV and CMV (Section 1.10). If any subject develops GVHD they will receive our standard GVHD treatment as per SOP F08.03.

2.5.2 GVHD Scoring

GVHD will be monitored for 6 weeks following infusion. Weekly GVHD organ stage scores, overall clinical grade, biopsy information for GVHD and relevant differential diagnosis will be recorded. The weekly score will encompass all information since the last assessment. Organ involvement, biopsy information, staging, differential diagnosis, and GVHD therapy will be documented in the medical record using the Blood and Marrow Transplant Clinical Trials Network (BMT CTN) GVHD scoring stamp or equivalent.

Clinical Acute GVHD Assessment													
Date _____			Patient ID _____				Karnofsky/Lansky _____						
CODES						DIFFERENTIAL DIAGNOSIS							
	0	1	2	3	4	5	GVHD	Drug Rxn	Cond Reg	TPN	Infect	VOD	Other
Skin													_____
Lower GI													Vol: _____
Upper GI													
Liver													Max bili: _____
Treatment:	 CSA		 Tacrolimus		 Pred		 Methylpred		 Ontak				
	 Pentostatin		 MMF		 Etanercept		 Other _____						
Code Definitions:													
Skin:			Lower GI (Diarrhea):			Upper GI:			Liver (Bilirubin):				
0 No rash			0 None			0 No protracted			0 < 2.0 mg/dl				
1 Maculopapular rash, < 25% of body surface			1 ≤ 500 mL/day or < 280 mL/m ²			nausea and vomiting			1 2.1-3.0 mg/dl				
2 Maculopapular rash, 25-50% of body surface			2 501-1000 mL/day or 280- 555 mL/m ²			1 Persistent nausea, vomiting or anorexia			2 3.1-6.0 mg/dl				
3 Generalized erythroderma			3 1001-1500 mL/day or 556- 833 mL/m ²						3 6.1-15.0 mg/dl				
4 Generalized erythroderma with bullous formation and desquamation			4 > 1500 mL/day or > 833 mL/m ²						4 > 15.1 mg/dl				
			5 Severe abdominal pain with or without ileus, or stool with frank blood or melena										
Signature _____													

CHARMS Protocol v1.0 (10.30.13)	Version 5.0 (10.6.15)
Version 2.0 (12.09.13)	Version 6.0 (08.29.16)
Version 2.1 (03.07.14)	Version 7.0 (04.26.17)
Version 3.0 (06.17.14)	Version 8.0 (05.24.17)
Version 4.0 (11.06.14)	Version 9.0 (08.10.17)

2.5.3 Chronic GVHD

Chronic GVHD will be assessed at 3, 6 and 12 months post-infusion. Assessment and a description of symptoms (only if GVHD is present) will be documented through completion of the GVHD symptom record (see Appendix I).

Definite and Possible Manifestations of Chronic GVHD

Organ System	Definite manifestations of chronic GVHD	Possible manifestations of chronic GVHD
Skin	Scleroderma (superficial or fasciitis), lichen planus, vitiligo, scarring alopecia, hyperkeratosis pilaris, contractures from skin immobility, nail bed dysplasia	Eczematoid rash, dry skin, maculopapular rash, hyperpigmentation, hair loss
Mucous membranes	Lichen planus, non-infectious ulcers, corneal erosions/non-infectious conjunctivitis	Xerostomia, keratoconjunctivitis sicca
GI tract	Esophageal strictures, steatorrhea	Anorexia, malabsorption, weight loss, diarrhea, abdominal pain
Liver	None	Elevation of alkaline phosphatase, transaminitis, cholangitis, hyperbilirubinemia
GU	Vaginal stricture, lichen planus	Non-infectious vaginitis, vaginal atrophy
Musculoskeletal/ Serosa	Non-septic arthritis, myositis, myasthenia, polyserositis, contractures from joint immobilization	Arthralgia
Hematologic	None	Thrombocytopenia, eosinophilia, autoimmune cytopenias
Lung	Bronchiolitis obliterans	Bronchiolitis obliterans with organizing pneumonia, interstitial pneumonitis

2.5.4 Other toxicities

Should unanticipated toxicities arise (e.g. severe local reactions or hepatorenal damage) they, too, will be graded by the NCI Common Terminology Criteria for Adverse Events (CTCAE), Version 4.X with the exception of CRS that is related to T-cell infusions. CRS will be graded according to Appendix II.

2.5.5 Management of Toxicity

VSTs are susceptible to killing by steroids given at a dose of 1-2mg/kg. This is standard therapy for GVHD and could also be given if a recipient develops other complications considered possibly related to VST administration. Anti TNF-alpha receptor antibody and anti IL-6 also may have some efficacy in individuals that develop SIRS after T cell infusion and may be considered in patients with consistent clinical signs/symptoms (see SOP: F05.11.4 MANAGEMENT OF

CHARMS Protocol v1.0 (10.30.13)	Version 5.0 (10.6.15)
Version 2.0 (12.09.13)	Version 6.0 (08.29.16)
Version 2.1 (03.07.14)	Version 7.0 (04.26.17)
Version 3.0 (06.17.14)	Version 8.0 (05.24.17)
Version 4.0 (11.06.14)	Version 9.0 (08.10.17)

ADVERSE REACTIONS TO CTL INFUSIONS for dosage details). Other supportive care would be per standard medical practice.

3 STUDY ENDPOINTS

3.1 Primary Endpoint

The primary objectives for this pilot study are feasibility and safety. Safety of administration of VSTs is 42 days for GVHD and 28 days for other toxicities. Except as noted below, the safety endpoint will be defined as acute GvHD grades III-IV within 42 days of the last dose of VSTs or grades 3-5 non-hematologic adverse events related to the T cell product within 28 days of the last VST dose and that are not due to the pre-existing infection or the original malignancy or pre-existing co-morbidities as defined by the NCI Common Terminology Criteria for Adverse Events (CTCAE), Version 4.X.

Grade 3 and 4 expected reactions seen with the use of T cell-based immunotherapy, such as fever and hypotension requiring pressor support, will not be considered a safety endpoint. Any other grade 3 or greater toxicity felt to be related to or resulting from Cytokine Release Syndrome (CRS) is included in the safety endpoint. Grade 3 and 4 CRS infusion reactions that are persistent beyond 72 hours will be reported to the FDA in an expedited fashion, and will be considered a treatment-limiting toxicity.

Toxicities to consider include GI toxicity, renal toxicity, hemorrhagic toxicity, cardiovascular toxicity (hypotension, cardiac arrhythmia and left ventricular systolic dysfunction), neurological toxicity (somnolence and seizure), coagulation toxicity, vascular toxicity and pulmonary toxicity.

3.1.1 Staging and Grading of Acute GVHD

Staging*

	Stage 0	Stage 1	Stage 2	Stage 3	Stage 4
Skin	No rash	Rash < 25% BSA	25-50%	> 50% Generalized erythroderma	Plus bullae and desquamation
Gut	< 500 mL diarrhea/day	501-1000 mL/day	1001-1500 mL/day	> 1500 mL/day	Severe abdominal pain & ileus
UGI		Severe nausea/vomiting			
Liver	Bilirubin ≤ 2 mg/dl	2.1-3 mg/dl	3.1-6mg/dl	6.1-15mg/dl	> 15 mg/dl

Acute GVHD grading should be performed by the consensus conference criteria (Przepiorka, et al., 1994).⁵⁹

Grading Index of Acute GVHD*

	Skin	Liver	Gut	Upper GI
0	None and	None and	None and	None
I	Stage 1-2 and	None and	None	None
II	Stage 3 and/or	Stage 1 and/or	Stage 1 and/or	Stage 1
III	None-Stage 3 with	Stage 2-3 or	Stage 2-4	N/A
IV	Stage 4 or	Stage 4	N/A	N/A

CHARMS Protocol v1.0 (10.30.13)	Version 5.0 (10.6.15)
Version 2.0 (12.09.13)	Version 6.0 (08.29.16)
Version 2.1 (03.07.14)	Version 7.0 (04.26.17)
Version 3.0 (06.17.14)	Version 8.0 (05.24.17)
Version 4.0 (11.06.14)	Version 9.0 (08.10.17)

3.1.2 Antiviral Activity

Peripheral blood and, where relevant, stool and urine will be monitored for CMV, EBV, adenovirus, BK virus, JC virus and/or HHV6 viral load. For the infection under treatment response in viral load will be defined as follows:

Complete response: Return to normal range as defined by specific assay used and clinical signs and symptoms.

Partial response: Decrease in viral load of at least 50% from baseline or 50% improvement of clinical signs and symptoms

Mixed response: Decrease in viral load of at least 50% from baseline for one infection and an increase or no change in viral load for a second infection (only applicable for patients with two or more infections at baseline).

Stable disease: Changes insufficient to qualify as partial response or progression

Progression: Increase in viral load of at least 50% from baseline or dissemination to other sites of disease.

Viral response data will be reviewed by a consensus committee of investigators.

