2.3 Eligibility

2.3.1 Inclusion Criteria

For Initial VSTs and subsequent infusions: patients will be eligible following any type of allogeneic transplant (*as defined 2.3.1.1*) if they have CMV, adenovirus, EBV, BK virus and/or HHV6 infection/disease persistent or recurrent despite 14 days of standard therapy (*as defined 2.3.1.2*) OR after failure of treatment (*as defined 2.3.1.2*) after 7 days of standard therapy OR if unable to tolerate standard therapy. Patients with persistent JC virus infection will be eligible as well.

1. Prior myeloablative or non-myeloablative allogeneic hematopoietic stem cell transplant using either bone marrow or peripheral blood stem cells or single or double cord blood.
2. Treatment of the following persistent or relapsed infections despite standard therapy;

a. CMV: Treatment of persistent or relapsed CMV disease or infection after standard therapy. For CMV infection, standard therapy is defined as antiviral therapy with ganciclovir, foscarnet or cidofovir.^{56,57}

- i. CMV disease: defined as the demonstration of CMV by biopsy specimen from visceral sites (by culture or histology) or the detection of CMV by culture or direct fluorescent antibody stain in bronchoalveolar lavage fluid in the presence of new or changing pulmonary infiltrates or changes consistent with CMV retinitis on ophthalmologic examination.
- ii. CMV infection: defined as the presence of CMV positivity as detected by PCR or pp65 antigenemia or culture from ONE site such as stool or blood or urine or nasopharynx.

Failure of antiviral therapy: defined as a rise or a fall of less than 50% in viral load in peripheral blood or any site of disease as measured by PCR or pp65 antigenemia after 7 days of antiviral therapy.

b. Adenovirus: Treatment of persistent adenovirus infection or disease despite standard therapy. Standard therapy is defined as antiviral therapy with cidofovir¹³ or an alternative antiviral agent if patient will not tolerate cidofovir therapy because of poor renal function.

CHARMS Protocol v1.0 (10.30.13)	Version 5.0 (10.6.15)
Version 2.0 (12.09.13)	Version 6.0 (08.29.16)
Version 2.1 (03.07.14)	Version 7.0 (04.26.17)
Version 3.0 (06.17.14)	Version 8.0 (05.24.17)
Version 4.0 (11.06.14)	Version 9.0 (08.10.17)

- i. Adenovirus infection: defined as the presence of adenoviral positivity as detected by PCR or culture from ONE site such as stool or blood or urine or nasopharynx.

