- ii. Adenovirus disease: defined as the presence of adenoviral positivity as detected by PCR, DFA or culture from two or more sites such as stool or blood or urine or nasopharynx.
- iii. Failure of therapy: defined as a rise or a fall of less than 50% in viral load in peripheral blood or any site of disease as measured by PCR or any other quantitative assay) after 7 days of antiviral therapy.

c. EBV: For treatment of persistent EBV infection despite standard therapy. For EBV infection, standard therapy is defined as rituximab given at 375mg/m² in patients for 1-4 doses with a CD20+ve tumor.⁵⁸

- i. EBV infection: defined as
 1. Biopsy proven lymphoma with EBV genomes detected in tumor cells by immunocytochemistry or in situ PCR
 2. Or clinical or imaging findings consistent with EBV lymphoma and/or elevated EBV viral load in peripheral blood.
- ii. Failure of therapy is defined as
 1. Increase or less than 50% response at sites of disease for EBV lymphoma OR
 2. Increase or a fall of less than 50% in EBV viral load in peripheral blood or any site of disease after 1st dose of rituximab.

d. BK virus: Treatment of persistent BK virus infection or BK virus disease despite antiviral treatment with cidofovir or leflunomide. No clear standard treatment is defined (section 1.1.5). Cidofovir¹⁵ has been administered in low doses as well as high doses to HSCT patients with BK infections but no randomized trials are available proving its clinical efficacy. In small trials leflunomide had activity against BK virus¹⁷, therefore we will consider this agent an acceptable alternative to cidofovir, given the absence of a clear first line option.

- i. BK virus infection is defined as the presence of BK virus positivity as detected by PCR or culture in one site such as blood or urine.
- ii. BK virus disease is defined as the presence of BK virus detectable by culture or PCR in blood or urine or other body fluids and symptoms of disease including, but not limited to persistent microscopic or macroscopic hematuria or detectable BK virus in more than one site.
- iii. Failure of therapy is defined as a rise or a fall of less than 50% in viral load in peripheral blood or any site of disease as measured by PCR or any other quantitative assay) or worsening hematuria after 7 days of antiviral therapy.

e. HHV6: Treatment of persistent HHV6 infection or disease despite antiviral treatment with ganciclovir, cidofovir and foscarnet. No clear standard treatment is defined.

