CHARMS Protocol v1.0 (10.30.13)	Version 5.0 (10.6.15)
Version 2.0 (12.09.13)	Version 6.0 (08.29.16)
Version 2.1 (03.07.14)	Version 7.0 (04.26.17)
Version 3.0 (06.17.14)	Version 8.0 (05.24.17)
Version 4.0 (11.06.14)	Version 9.0 (08.10.17)

Ganciclovir, cidofovir and foscarnet all have variable *in vitro* activity against HHV-6, and may have a role in treating HHV-6-associated disease – therefore antiviral treatment with one or more of these agents will be acceptable initial therapy.

- i. HHV6 virus infection is defined as the presence of elevated HHV-6 levels as detected by PCR or positive culture in one site such as CSF or blood.
- ii. HHV6 disease is defined as defined as the presence of HHV6 detectable by culture or PCR in one or more sites such as blood or CSF and symptoms of disease including symptoms of HHV6 encephalitis OR detectable HHV6 by PCR or culture in more than one site.
- iii. Failure of therapy is defined as a rise or a fall of less than 50% in viral load in peripheral blood or any site of disease (as measured by PCR or any other quantitative assay) after 7 days of antiviral therapy.

f. JC virus: Treatment of progressive or persistent JC virus infection or disease without suitable alternative treatment option. Pepmixes specific for antigens on adenovirus, EBV, CMV, HHV6 and BK virus are used to generate our multivirus-specific VSTs. No pepmix specific for the rare JC virus is used for generation of these CTLs, however given the high homology (>90%) between JC and BK and the fact that BK virus-specific T cells targeting VP1 and Large T (as targeted in our multivirus VSTs) have been administered to treat JCV-PML, resulting in viral clearance from the cerebrospinal fluid it is likely that our VSTs are efficacious against JC virus. Given the current lack of treatment options for JC virus infection or reactivation after HSCT and the risk of progression to JML, which is almost uniformly fatal, and the apparent activity of BK virus-directed T cells against JC virus infected cells, we propose including patients with progressive or persistent JC virus on this study, unless a suitable alternative therapy is available.

- i. JC virus infection is defined as the presence of elevated JC virus levels as detected by PCR or positive culture in one site such as CSF or blood.

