3.1.5 Effects on Clinical Signs of Viral Infection

If a patient has organ involvement clinical response will be monitored. For patients with EBV lymphoma and measurable disease, response will be assessed by RECIST criteria.

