5.2 Sample Size Determination and Design Characteristics

Frist, the study will conduct a single arm pilot study using a phase IIa design. Simon's two-stage Minimax design⁶⁰ will be used to for the single-arm pilot study. Under the null hypothesis that the VST is not active, the data from previous trials suggest that the true response rate is 20% in anti-viral activity, where a positive response is defined as the viral load reduction to the normal level for at least one of the 5 virus types (CMV, EBV, adenovirus, BK virus and HHV6) within 42 days following the initial treatment of VST.

Allowing a 5% type-I error and 90% power, the null hypothesis will be tested against a one-sided alternative that the true response rate is 40%. The maximum size is 45 eligible patients, defined as the patients who receive the VST infusion and who can finish the 42 days follow-up. We anticipate that most patients will finish the follow up and will allow a 10% drop out rate. Therefore, the maximum sample size is 50.

The phase IIa trial operates in two stages, where the first stage recruits 24 patients. The trial pauses at the end of the first stage to make the decision on whether to stop the trial early due to lack of enough efficacy for treating viral infection, according to the rule as follows. Of the 24 patients at the first stage, if 5 or fewer positive responses are observed, then the study will be stopped. Otherwise, 21 additional patients will be accrued to reach the goal of 45 accruals. At the end of the trial, the null hypothesis will be rejected, if 14 or more positive responses are observed in among the 45 patients. This design has 65.6% chance to stop early when the true response rate is 20%.

After the phase IIa trial suggests excellent clinical responses that warrant further investigation, the study will be expanded to recruit 30 additional patients to evaluate the viral reduction based HLA matching. We hypothesize the viral reduction among the low HLA matching group (1/8, 2/8, or 3/8 HLA matching) is not worse than the high HLA matching group (4/8, 5/8, 6/8, 7/8, or 8/8).

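### The Simon responder in 5.2 is viral load only, so eligible patients with no abnormal load in blood, stool or urine count in the 24/45 but cannot respond

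*Combined protocol and SAP*

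**What the plan says.** **Entry (2.3.1).** Several routes need no abnormal load in blood, stool or urine:
- CMV disease may rest on "demonstration of CMV by biopsy specimen from visceral sites", on culture or antibody staining of "bronchoalveolar lavage fluid in the presence of new or changing pulmonary infiltrates", or on a retinal examination.
- CMV or adenovirus infection needs one positive site, and the nasopharynx is among the examples.
- EBV may be biopsy-proven lymphoma, or "Or clinical or imaging findings consistent with EBV lymphoma and/or elevated EBV viral load in peripheral blood". The and/or lets imaging stand alone.
- HHV6 infection is the "presence of elevated HHV-6 levels as detected by PCR or positive culture in one site such as CSF or blood".

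**Monitoring (3.1.2, 3.1.5).** On viral load, "Peripheral blood and, where relevant, stool and urine will be monitored for CMV, EBV, adenovirus, BK virus, JC virus and/or HHV6 viral load". Complete response in 3.1.2 combines the assay's normal range with clinical signs and symptoms, and a committee of investigators reviews viral response data. Section 3.1.5 follows clinical response where an organ is involved, and "For patients with EBV lymphoma and measurable disease, response will be assessed by RECIST criteria".

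**Decision rule (5.2).** For the Simon design, "a positive response is defined as the viral load reduction to the normal level for at least one of the 5 virus types", within 42 days of the first infusion. The denominator is every infused patient who completes 42 days. The phase IIa part stops at 5 or fewer responders in 24 and rejects a 20% rate at 14 or more in 45. The rule names no specimen, sets no baseline requirement and has no clinical or imaging component.

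**The concern.** The rule can only credit a fall from an abnormal load to a normal one. A patient with EBV lymphoma and a normal blood load, CMV retinitis without viraemia, or adenovirus confined to the nasopharynx has no abnormal load to reduce in the specimens that 3.1.2 names. The lymphoma or retinitis could resolve completely, and 3.1.5 would record it, yet the patient would still count as a failure in the stop/continue decision.

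Antiviral response is a secondary endpoint. Feasibility and safety are primary. But this count decides whether phase IIa stops at 24, and its result bears on the expansion by 30 patients. Structural non-responders pull the observed rate down for a reason unrelated to the product.

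A second gap is smaller. Adenovirus disease is defined by two or more positive sites, and BK disease can involve more than one. When one virus is positive in several specimens, the plan does not say which result decides response.

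**Working it through.** **Inputs (5.2).** Null rate 20%, alternative 40%, one-sided 5% type I error, 90% power; 24 then 21 patients; stop at 5 or fewer; reject at 14 or more of 45; 10% drop-out.

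**Formulas.** With X ~ Bin(24, p) and Y ~ Bin(21, p):
- P(stop early) = P(X ≤ 5)
- P(reject) = Σ over x = 6 to 24 of P(X = x) · P(Y ≥ 14 − x)

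**Step 1: reproduce the plan.** At p = 0.20, P(stop early) = 65.6%, as stated, and P(reject) = 4.8%. At p = 0.40, P(reject) = 90.0%. Drop-out: 45/0.90 = 50. The plan's arithmetic is correct, so the issue is the endpoint definition.

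**Step 2: effect of built-in non-responders.** Let f be the share of the 45 with no abnormal load in a monitored specimen. The documents do not give f, so the values below are assumptions. These patients are taken to fall at random across the two stages. The effective response rate is p(1 − f).

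| f | Expected in 45 (45f) | Rate if truth is 40% | Early stop at that rate | Power | Type I error, p = 0.20(1 − f) |
|---|---|---|---|---|---|
| 0 | 0 | 40.0% | 4.0% | 90.0% | 4.8% |
| 2% | 0.9 | 39.2% | 4.7% | 88.1% | 4.2% |
| 5% | 2.25 | 38.0% | 6.0% | 84.6% | 3.3% |
| 10% | 4.5 | 36.0% | 8.7% | 77.5% | 2.1% |
| 15% | 6.75 | 34.0% | 12.4% | 68.6% | 1.3% |

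**Step 3: what exclusion does to the design.** If such patients leave the Simon set and no more than 50 are infused, the number assessable may fall below 45. Keep the first stage at 24 with the same stop rule, replace 21 by n − 24, and take the lowest final cut-off that holds type I error at or below 5%:

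| Assessable n | Final cut-off | Type I error | Power at 40% |
|---|---|---|---|
| 45 | 14 | 4.8% | 90.0% |
| 44 | 14 | 4.1% | 88.4% |
| 43 | 14 | 3.5% | 86.5% |
| 42 | 14 | 2.9% | 84.2% |
| 41 | 13 | 4.9% | 88.3% |
| 40 | 13 | 4.2% | 86.2% |

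The cut-off matters. At n = 41 or 40, keeping 14 gives power of 81.6% or 78.4%, so exclusion alone recovers little.

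**The case against.** The best defence is that few patients are affected. The synopsis requires the treated virus to be followed by PCR, and Table 4.2.2 lists viral load for previously positive viruses. For CMV, adenovirus, BK and HHV6, treatment failure is defined mainly by a quantitative load, so the plan presupposes a measurable load in most patients. This stands as a reason to expect a small f. It does not close the gap. Entry is also open through 14 days' persistence or intolerance, failure may be measured at any site of disease, and EBV lymphoma can qualify with no load at all.

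In the sponsor's earlier three-virus third-party study, 9 of 50 patients were treated for EBV-PTLD. How many lacked a raised blood load is not stated, and that study did not target BK or HHV6, so it does not fix f.

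Three stronger readings are tempting, but the documents do not support them:
- A reader might infer that response at these sites goes unmonitored. Sections 3.1.2 and 3.1.5 do follow clinical signs and apply RECIST. What is missing is a link to the Simon count.
- A reader might infer that a normal post-infusion load makes such a patient an automatic responder and inflates type I error. Section 5.2 asks for a reduction to normal and 3.1.2 for a return to it. A load that was never raised can do neither.
- A reader might infer that clearing one of several positive specimens is enough. In 5.2 the words about at least one refer to virus types. On several specimens of one virus the plan is silent.

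The consensus committee could settle individual cases, but the plan gives it no rule for them, and its members are investigators in a single-arm trial.

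**Conclusion.** The mismatch between entry and the Simon responder is real and should be corrected. Read plainly, its effect is a loss of power and a greater chance of stopping an active product. At a true 40% rate in the assessable patients, power is 88.1% if 2% are affected and 68.6% if 15% are. Type I error stays under 5% throughout. These figures rest on assumed shares, because the documents give none, and on the plain reading that an unraised load cannot be reduced to normal. Many patients with tissue, CSF or nasopharyngeal disease may also have an abnormal load in blood, stool or urine, in which case the loss is at the small end. The silence on multiple specimens is an ambiguity to close; its direction cannot be determined from the text.

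**What to change.** In 5.2:
1. Define the Simon-evaluable set, for both the 24 and the 45, as infused patients who finish 42 days and whose pre-infusion sample shows at least one treated virus, among the five, above the assay's normal range in a monitored specimen. This also settles patients treated only for JC virus, who are eligible although JC is not one of the five types.
2. State, before the interim look, which specimen or specimens decide response for each virus.
3. Keep all other patients in the safety analysis and report their response under 3.1.5.
4. Count non-assessable patients against the existing 10% allowance (5 of 50), with no replacement beyond 50 infused. If fewer than 45 are assessable, restate the power and apply a final cut-off fixed in advance for the number attained, as tabulated above.
5. Report the response rate in all infused patients as a sensitivity analysis.

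Set membership depends only on a pre-infusion measurement and the 42-day completion that 5.2 already requires. Section 4.2.2 already collects pre-infusion loads by virus; the specimens should be named there too. Eligibility and treatment do not change.

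The cost is slightly fewer evaluable patients and slightly lower stated power: 84.2% to 88.4% if 40 to 44 are assessable. Full replacement is not free, even though the study maximum is 80. With 10% drop-out it needs 45/(0.90 × 0.95) = 52.6, so 53 infused at f = 5%; 45/(0.90 × 0.90) = 55.6, so 56 at 10%; and 45/(0.90 × 0.85) = 58.8, so 59 at 15%. Each exceeds the phase IIa cap of 50, where the toxicity boundary table in 5.3 ends.
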